4.0 Test Schedule

Assessments, tests and procedures	Treatment			Observation ⁷
	Baseline ²	Last day of treatment (+/- 2 days)	12 weeks (+/- 8 weeks) post-radiation	12 months (+/- 3 month) post completion of radiotherapy, 24 months (+/- 3 months), 36 months (+/- 3 months), and at 5 years (+/- 3 months)
History and Physical exam (including breast assessment/exam) ¹	X	X	X	X
Mammogram	X ¹⁰			X ¹¹
Cosmesis ,QOL Outcome Assessment and Breast-Q ¹⁶ (see section 11.3 and Appendix)	X ¹³	X	X	X
Digital Photograph	X	X	X	X
Review of surgical specimen(s) to confirm eligibility	X ³			
Echocardiography ^{9, 14}	X ¹³			X ⁸
Radiation toxicity assessment (see section 10.4)	X	X	X	X
Serum pregnancy test	X ⁴			
Blood specimen ^{5, 17, R}	X ¹⁵	X	X	X ¹²
Surgical tumor specimen ^{6, 18, R}	X			

1. A general history & physical must be done \leq 8 weeks prior to registration. This should include an assessment of ECOG performance status (see Appendix I).

2. Following definitive surgical resection and adjuvant chemotherapy if indicated, prior to the start of radiation.
3. Outside pathology must be reviewed at the treating institution.
4. For women of childbearing potential only, must be within 7 days of radiotherapy
5. See section 14 for collection time and preparation of samples
6. See section 17 for collection time and preparation of samples
7. Patients that cannot come back to Mayo Rochester within the time constraints of the follow-up schedule; efforts to obtain outside records and send QOL's to be completed will occur, however the required items may not be captured.
8. Ideally 6-12 months post radiotherapy in HER2 positive patients treated with HER2 directed therapy and in patients treated with anthracycline as part of routine clinical care. Only followed for Echos 1 year post therapy.
9. Co-enrollment on IRB 15-007443 (echo protocol) is required in Rochester while open
10. Completed \leq 12 months prior to study entry
11. As clinically indicated
12. At 12 months post-treatment visit only to coincide with echocardiography.
13. Should be \geq 14 days since last chemotherapy
14. After closure of IRB 15-007443 (echo protocol) echocardiography tests will be performed only in left sided patients previously treated with anthracycline and/or HER2 directed systemic therapy. This correlative component will occur at Rochester Mayo only.
15. Baseline blood collection will be drawn through co-enrollment on IRB 15-000136 (Radiation Oncology Outcomes Registry and Biobanking Study).

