14.0 Body Fluid Biospecimens

- 14.1 Summary Table of Research Blood and Body Fluid Specimens to be Collected for this Protocol

Collection Tube	Volume to Collect per Tube (Number of Tubes to Collect)	Timepoint: Last day of treatment (+/- 2 days)	Timepoint: 12 weeks post-radiation (+/- 2 days)	Timepoint: 12 months post-treatment visit (+/- 3 months)
EDTA tubes	10 mL (1)	X	X	X
No additive tubes (for Serum)	10 mL (1)	X	X	X

The baseline sample will be obtained through co-enrollment in Radiation Oncology Patient Outcomes Registry and Biobanking Study, IRB#15-00136. All other samples will be drawn according to the test schedule and summary table above. Collect and process last day of treatment, 12 weeks post-radiation, and 12 months post-treatment, blood/blood products according to table 14.1. Label specimen tube(s) with protocol number, study patient ID number, and time and date blood is drawn.

- 14.2 BAP will process and store specimens per standard operating procedures.
- 14.3 Bloods will be collected prospectively and stored until funding sources have been

secured to investigate exploratory analyses described in section 16.64

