the presence of postoperative breast complications, higher dose (including radiotherapy boost), inhomogeneity, and use of concurrent chemotherapy.[43-45] We will analyze clinical and dose volume parameters correlated with increased risk of fibrosis and reconstruction failure following proton radiotherapy. However, clinical and dose-volume factors alone are not sufficient to explain the patient to patient variation in late toxicity following a course of radiation therapy.[46, 47] Indeed, patient specific molecular and genomic features may also be of significant importance in determining variation in normal tissue radiation response following breast cancer radiotherapy.

Cytokines and growth factors are involved in the radiation response and tissue remodelling and may serve as predictive factors for normal tissue damage. For example, levels of transforming growth factor β 1 (TGF- β 1) vary substantially between individuals and has previously been associated with radiation fibrosis in early-stage breast cancer patients.[48] TGF- β 1 is a multi-functional cytokine that attracts fibroblasts and stimulates collagen production.[49] Although basal levels may be important, expression levels of this protein are induced within an hour or less after exposure to ionizing radiation and therefore TGF- β 1 induction following radiation may be a better functional marker of an elevated fibrotic response.[50, 51] Therefore, blood will be drawn pre-treatment and on the last day of radiotherapy 1 hour following the final fraction. The pre and post radiotherapy levels of TGF- β 1 and other proteins in the fibrotic response will be compared and correlated with toxicity.

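### The collection tables allow the end-of-treatment blood draw two days either side of the last treatment day and do not carry over the 1-hour post-fraction timing that the TGF-β1 induction analysis calls for

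*Combined protocol and SAP*

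**What the plan says.** Section 16.643 (Molecular and Genomic Predictors of Fibrosis and Reconstruction Toxicity) argues that TGF-β1 induction may be a better functional marker than the basal level. Its reason is that "expression levels of this protein are induced within an hour or less after exposure to ionizing radiation". From this it derives the sampling rule: "blood will be drawn pre-treatment and on the last day of radiotherapy 1 hour following the final fraction". The planned use follows: "The pre and post radiotherapy levels of TGF- β 1 and other proteins in the fibrotic response will be compared and correlated with toxicity".

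The collection instructions are elsewhere. In the section 4.0 test schedule the post-radiation blood specimen sits in the column "Last day of treatment (+/- 2 days"), and footnote 5 to that row reads "See section 14 for collection time and preparation of samples". Table 14.1 then gives the same window: "Timepoint: Last day of treatment (+/- 2 days"). The text under it says "All other samples will be drawn according to the test schedule and summary table above", and asks staff to "Label specimen tube(s) with protocol number, study patient ID number, and time and date blood is drawn".

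Three further statements set the scale. Footnote 17 of section 4.0 limits post-radiation blood to the Rochester site. Section 14.3 says the blood is stored until money is found for the exploratory work in section 16.64. Footnote 4 of section 18.1 repeats a two-day tolerance for the post-radiation time point.

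**The concern.** The protocol itself ties the timing of this sample to the biology it wants to measure: because induction is fast, the draw should come 1 hour after the last exposure. The instructions that staff would follow to take the blood do not contain that rule. They name a day and a tolerance, with no hour and no order of fraction and draw. A coordinator could comply fully with sections 4.0 and 14 and never meet the 1-hour requirement.

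What is at stake is the meaning of the post-radiotherapy value in the pre/post comparison. If some samples come 1 hour after the final fraction, some before it and some two days later, the change from baseline mixes different times since irradiation, and its correlation with toxicity carries that extra variation. The samples are banked for later assay, so the timing cannot be corrected once the blood has been drawn.

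**Working it through.** The plan gives no figure to reproduce here. The check sets the sections side by side and then does simple window arithmetic.

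**Side by side**

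| Item | Section 16.643 | Sections 4.0 and 14.1 |
|---|---|---|
| Nominal day | Last day of radiotherapy | Last day of treatment |
| Tolerance | None stated | ± 2 days |
| Hour relative to fraction | 1 hour after the final fraction | Not stated |
| Fraction must precede draw | Yes | Not stated |
| Draw time recorded | Not stated | Yes, on the tube label |
| Clock time of final fraction recorded | Not stated | Not requested |

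The nominal day agrees. The tolerance, the hour and the order do not.

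**Which text governs collection.** Footnote 5 of section 4.0 sends staff to section 14 for collection time. Section 14 sends them back to the schedule and its own table. Its only pointer to section 16.64 (in 14.3) concerns which stored-sample analyses await funding, not when to draw. So the tables govern.

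**Distance from the target.** Put the final fraction at 0 h and the target at +1 h, and read ± 2 days as ± 48 h.

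- Earliest compliant draw: −48 h. Distance from target = −48 − 1 = −49 h.
- Latest compliant draw: +48 h. Distance from target = 48 − 1 = +47 h.

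Counted in calendar days, the window runs from −2 to +2, which is 5 days. Of these, 5 − 1 = 4 are not the last day of radiotherapy. On the one day that is, a draw before the fraction still meets both tables.

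**What cannot be calculated.** To turn these distances into a loss of signal one would need the time course of TGF-β1 after its rise and the spread of actual draw times. The documents give only the onset, an hour or less. They give no peak, no duration and no estimate of how many draws would be off target.

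**The case against.** The strongest reply is that the sections are compatible. Both tables tie the draw to the day of the final fraction, and a draw 1 hour after it satisfies all three places. The window permits off-target samples but does not require them. Section 16.643 could be read as narrowing the tables for this purpose. The first part stands. The last does not, because section 14 names the schedule and its own table as the source for draw times, and neither mentions the hour.

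There is also a partial safeguard. The tube label carries the date and time of the draw, and section 18.1 lists a radiation therapy form at end of treatment. If that form records the last treatment date (an assumption, since its fields are not shown), draws on the wrong day could be found and set aside. This stands for wrong-day draws. It does not settle the order or the interval within the day, because no clock time for the fraction is requested.

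A third reply is that an off-target draw need not miss induction. Treatment is daily, so a sample taken after an earlier day's fraction could still show a response to that fraction. A late sample might also still be raised. Both are possible on the documents. Neither would be the sample that section 16.643 describes.

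Three stronger readings are tempting and should not be drawn:

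- *A reader might infer that the induction hypothesis cannot be tested.* The documents do not support this. Samples drawn on time remain usable, and nothing says how many will be mistimed.
- *A reader might infer an imbalance between arms.* Suppose fractions fall on consecutive days and a draw comes two days early, after that day's fraction. Two fractions are then outstanding: 2/25 = 8.0% of the course in Arm 1 and 2/15 = 13.3% in Arm 2. These are shares of the course still to be given, not a difference in draw timing. The window is the same in both arms, and the documents give no mechanism by which timing would differ.
- *A reader might set the full width of the window, 2 × 48 = 96 h, against 1 h.* This compares a width with a target time. The distances of 49 h and 47 h are the correct description.

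**Conclusion.** The point holds as an internal inconsistency in the timing of one research sample. Section 16.643 states a requirement, derived from its own rationale, that the governing tables do not carry. The permitted departure is about 49 h early to 47 h late, and includes draws before the final fraction. The effect is added timing variation in the TGF-β1 pre/post comparison.

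The conclusion rests on reading ± 2 days as ± 48 h around the final fraction, and on section 14 governing collection as it says it does. How much information would be lost is unknown, because the documents do not say how long levels stay raised.

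The importance is minor. The work is exploratory, unfunded when the plan was written and confined to Rochester for post-radiation blood. No primary or safety result depends on it.

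**What to change.** Reconcile sections 4.0, 14.1 and 16.643:

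1. In the section 4.0 schedule and table 14.1, state that the end-of-treatment research blood is drawn 1 hour after the final fraction, with a stated tolerance in minutes or hours.
2. Record the clock time of the final fraction beside the draw time already required on the tube label, so that time since irradiation can be calculated for every sample.
3. In section 16.643, limit the TGF-β1 induction analysis to samples within that tolerance, and report how many fall outside it.
4. Keep the ± 2 day window for the other markers, such as the cardiac markers, which section 16.641 ties only to the section 4.0 schedule. A mistimed sample is then still banked and used. Section 16.643 also names other fibrotic-response proteins without giving their induction time, so it should say which window applies to them.

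The cost is table wording and one extra time field, with no added visit or tube. The downside is that some samples will fall outside the tolerance and be excluded from this one analysis.

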16.7 Data & Safety Monitoring

16.71 Data and Safety Monitoring Plans: The Mayo Clinic Cancer Center (MCCC) Data Safety and Monitoring Board (DSMB) is responsible for reviewing the accrual and safety for this trial at least twice a year, based on reports provided by the MCCC Statistical Office..

16.72 Adverse Event Stopping Rules: The stopping rules specified below are based on knowledge available at study development. We note that the Adverse Event Stopping Rule may be adjusted in the event of either (1) the study re-opening to accrual or (2) at any time during the conduct of the trial and in consideration of newly acquired information regarding the adverse event profile of the treatment(s) under investigation. The study team may choose to suspend accrual because of unexpected adverse event profiles that have not crossed the specified rule below. The following rule will be evaluated for each arm separately.

Accrual will be temporarily suspended if at any time we observe events considered at least possibly related to study treatment (i.e. an adverse event with attribute specified as “possible,” “probable,” or “definite”) that satisfy one of the following:

- If 3 or more patients in the first 15 treated patients experience a grade 3 or higher adverse event, besides acute dermatitis, that is at least possibly related to treatment within 90 days post treatment.
- After the first 15 patients have been treated: if $\geq 20\%$ of all patients experience a grade 3 or higher adverse event, besides acute dermatitis, that is at least possibly related to treatment within 90 days post treatment.

We note that we will review grade 4 and 5 adverse events deemed “unrelated” or “unlikely to be related”, to verify their attribution and to monitor the emergence of a previously unrecognized treatment-related adverse event.

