10.41 Grading Scale for other toxicities

Telangiectasia: Grade 0 – None; Grade 1 – 1cm²; Grade 2 – 2-4cm²; Grade 3 - >4cm²

10.5 Submit via appropriate *reporting mechanisms* the following AEs experienced by a patient and not specified in Section 10.4:

10.52 Grade 3 and 4 AEs regardless of attribution to the study treatment or procedure.

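### Section 16.72 exempts acute dermatitis of any grade from accrual suspension, and its grade 4-5 review covers only events judged unrelated or unlikely related, so treatment-related grade 4-5 acute dermatitis meets no pre-specified trigger or grade 4-5 review

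*Combined protocol and SAP*

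**What the plan says.** Section 16.72 (Adverse Event Stopping Rules, under 16.7) opens its rule with "Accrual will be temporarily suspended if at any time we observe events considered at least possibly related to study treatment", meaning an attribution of possible, probable or definite. It also states: "The following rule will be evaluated for each arm separately".

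There are two triggers:

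- Early: "If 3 or more patients in the first 15 treated patients experience a grade 3 or higher adverse event, besides acute dermatitis", at least possibly related and within 90 days after treatment.
- After the first 15 patients: 20% or more "of all patients experience a grade 3 or higher adverse event, besides acute dermatitis, that is at least possibly related to treatment within 90 days" after treatment.

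The closing note of the section says "we will review grade 4 and 5 adverse events deemed" to fall in one of the two lowest attribution categories (unlikely or unrelated). Its stated aim is "to verify their attribution and to monitor the emergence of a previously unrecognized treatment-related adverse event".

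The same section lets the study team suspend accrual for unexpected adverse event profiles that have not crossed the rule, allows the rule to be adjusted during the trial, and has the DSMB review safety at least twice a year. Section 10.4 lists radiation dermatitis among the events graded by CTCAE at baseline and at each evaluation.

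**The concern.** The words exempting acute dermatitis carry no grade in either trigger, so grades 4 and 5 are exempt along with grade 3. The closing note is the only place in 16.72 that singles out grades 4 and 5, and it looks only at events judged not to be caused by treatment. A grade 4 or 5 acute dermatitis attributed to radiotherapy is named out of the first provision and, because it is related, falls outside the second.

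The documents give no reason for the exemption. A plausible one is that skin changes are common (section 9.0) and would otherwise dominate the count. That reason does not obviously reach life-threatening or fatal dermatitis. At stake is whether a cluster of such events in one arm would suspend accrual by rule or only by judgement, in a trial whose stated aim is to determine safety.

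**Working it through.** **1. The provisions side by side, for a treatment-related grade 4-5 acute dermatitis**

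| Provision | Reaches the event? | Threshold? |
|---|---|---|
| 16.72, first 15 patients | No, exempt at every grade | 3 patients |
| 16.72, after 15 patients | No, exempt at every grade | 20% |
| 16.72, closing grade 4-5 review | No, unrelated or unlikely related only | None |
| 16.1, primary endpoint | No, late events only; 16.2 starts these after 90 days | Not a monitoring rule |
| 8.0, dose modifications | No pre-specified interruptions for adverse events | None |
| 10.4, solicited grading | Yes | None |
| 10.1 and 10.3, SAE reporting, and IRB report within 5 working days if a UPIRTSO | Yes, if criteria are met | None |
| 10.61, regular assessment of SAE number and type | Yes, if an SAE | None |
| 10.62 and 16.71, DSMB at least twice a year | Yes | None |
| 16.72, discretionary suspension | Yes, if the profile is judged unexpected | None |

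Every row that has a suspension threshold excludes the event, and every row that includes it has no threshold.

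**2. The plan's own threshold**

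3/15 = 0.20, so the early and later triggers agree. The plan states no operating characteristics for this rule.

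**3. Current text**

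Related grade 4-5 acute dermatitis adds 0 to the count at any rate. Even 15 of 15 patients in one arm would not trip the rule on that ground.

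**4. If these events were counted**

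Inputs: 82 patients to be treated (16.4), randomized 1:1, so 82/2 = 41 per arm. True rate p is assumed.

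First-15 trigger alone: P(X ≥ 3), X ~ Binomial(15, p).

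Whole rule: let c(n) be the number of patients with an event among the first n. The rule fires if c(n) ≥ 3 for some n ≤ 15, or c(n) ≥ 0.20n for some n from 16 to 41. (The second threshold is 4 patients at n = 16-20, 5 at 21-25, and so on up to 9 at 41.) The probability comes from the recursion P(n, c) = P(n−1, c)(1−p) + P(n−1, c−1)p, removing states that have fired.

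| Assumed p | First 15 only | Whole rule, 41 patients |
|---|---|---|
| 1% | 0.04% | 0.04% |
| 3% | 0.9% | 1.0% |
| 5% | 3.6% | 4.1% |
| 10% | 18.4% | 23% |
| 20% | 60.2% | 78% |
| 30% | 87.3% | 98% |

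Simulation of the whole rule agrees (0.05%, 1.1%, 4.1%, 23%, 78%, 98%).

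**5. Added to other related grade 3 or higher events**

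Assume a rate q for the other events, a rate d for grade 4-5 dermatitis, and independence. The combined rate is u = 1 − (1−q)(1−d). With q = 3%, the first-15 trigger fires 0.9% of the time under the current text, whatever d is. With dermatitis counted it fires 2.0%, 5.5%, 10.8% and 29.5% of the time at d = 1%, 3%, 5% and 10%. For q from 1% to 10%, the current figure runs from 0.04% to 18.4%, and at d = 10% it would run from 22.0% to 56.4%.

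**6. A review that acts on any single event**

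P(at least one event in 41) = 1 − (1−p)^41. This gives 1 − 0.99^41 = 34% at 1%, 1 − 0.97^41 = 71% at 3%, and 1 − 0.95^41 = 88% at 5%.

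**The case against.** The strongest reply is that such an event would hardly go unnoticed. Dermatitis is graded at every evaluation. Death and life-threatening events are SAEs, whose number and type are assessed regularly. The DSMB meets at least twice a year, and the study team may suspend accrual for unexpected profiles that have not crossed the rule. All of this stands. A reader might infer from 16.72 that related grade 4-5 dermatitis escapes safety oversight altogether; the documents do not support that. What is missing is narrower: a pre-specified threshold or grade 4-5 review that includes it.

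Two further inferences should also be resisted.

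- Section 10.5 asks for submission only of events not listed in 10.4, which might look like a gap in data capture. It is not one: dermatitis is solicited under 10.4, and section 18.1 has a form for solicited adverse events at end of treatment and at 12 weeks.
- One might argue that larger fractions make severe acute dermatitis a particular risk of the 15-fraction arm. Section 1.3 says the opposite about tissue type: it gives skin desquamation a high α/β ratio and reserves marked fraction-size sensitivity for late-responding tissue. With its formula BED = nd(1 + d/(α/β)) and the section 7.3 doses, the 25- and 15-fraction schedules give 50(1 + 2/4.7) = 71.3 and 40.05(1 + 2.67/4.7) = 62.8 at α/β 4.7, and 78.6 and 70.6 at 3.5. The 15-fraction arm is lower at both.

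It is also fair to say that a 20% threshold detects rare events poorly, so counting them would seldom change whether accrual stops. That limits the size of the point. The exemption is narrow, too: it names acute dermatitis only, so breast infection and other skin terms still count.

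**Conclusion.** The point holds as a limited gap in the wording of 16.72. Treatment-related grade 4-5 acute dermatitis contributes nothing to the only count that automatically suspends accrual, and it is outside the section's grade 4-5 review. It remains monitored through routes that carry no threshold. Three such events among the first 15 patients of an arm would not suspend accrual automatically; a reader should not take this to mean that accrual would necessarily continue.

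The practical size depends on a rate the documents do not give. Counting the events would make the rule fire on them alone about 4% of the time or less at true rates up to 5%, and 23% at 10%. The high firing probabilities at 20% and 30% rest on rates that nothing in the documents makes plausible. The figures assume 41 patients per arm, evaluation after each patient, and independence between patients. The reading of the text does not depend on them. This is a cheap improvement, not a serious defect.

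**What to change.** The sponsor should state whether the exemption is meant to reach grades 4 and 5. If it is not, either of two edits to 16.72 closes the gap:

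- In both triggers, replace *besides acute dermatitis* with *besides grade 3 acute dermatitis*.
- Extend the closing grade 4-5 review to include related grade 4-5 acute dermatitis.

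The first gives a threshold but rarely fires when events are rare. The second has no threshold but would look at every single event, and so suits rare events better. They can be combined.

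Both concern accrual monitoring, not patient treatment. The grades are already collected, and 16.72 itself allows the rule to be adjusted. The cost is a short amendment, plus for the first edit a small added chance of suspension: on these events alone, about 0.04% at an assumed 1% rate, 1% at 3%, 4% at 5% and 23% at 10%.

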16.4 Sample Size Determination

The proposed trial design is a randomized phase II trial with a 1:1 randomization ratio with the stratification variable noted in section 5.1. The primary endpoint for this trial is the 24-month complication rate, as defined above. The study will plan to enroll a total of 72 evaluable patients. An evaluable patient is defined as a patient who receives any dose of the protocol-defined radiotherapy. In this trial, we will accrue and randomize up to 96 patients over 3 years to account for ineligibility, cancellations (withdrawals prior to protocol therapy), major treatment violations, or other reasons, and treat a total of 82 patients in order to ensure 72 evaluable patients at 24 months.

This study is designed as a non-inferiority/superiority “hybrid” design using the approach of Freidlin et al.[36] It is estimated that approximately 2/3 of the patients will undergo reconstruction. For patients who undergo mastectomy with immediate reconstruction, the rate of unplanned surgical complications at the Mayo Clinic is ~15% (personal communications with [name] and [name] 6/2014), comparable to what has been reported in the literature in the modern era.[27]. The rate of grade 3 or greater late toxicity in this population is expected to be $\leq 1\%$ (Whelan ASCO 2011). For the purpose of designing this trial, we will assume a 10% complication rate in the control arm. We consider that a 10% increase of this rate in the experimental arm would be acceptable (i.e. a non-inferiority margin of 10%). Based on the results of the START-B clinical trial[9], it is also plausible that toxicities in the experimental arm may even be reduced with the shortened fractionation schedule. Therefore, a marginal *decrease* in complication rate in the experimental arm to 5% (i.e. marginal benefit margin of 5%) may be reasonably expected. Denote p_0 and p_1 as the 24-month complication rate in the control arm and experimental arm, respectively. The null hypothesis is that the complication rate in the experimental arm is inferior to the control rate of 10% by more than 10% (i.e. $H_0: p_1 - p_0 > 10\%$). The alternative hypothesis is that the complication rate in the experimental arm is non-inferior to the control rate of 10% (i.e. $H_A: p_1 - p_0 < 10\%$).

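### The accrual-suspension rule in 16.72 gives a related death no more weight than a grade 3 event, so two related deaths in an arm's first 15 patients do not require suspension

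*Combined protocol and SAP*

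**What the plan says.** Section 16.72 of the combined protocol and SAP opens its rule with "Accrual will be temporarily suspended if at any time we observe events considered at least possibly related to study treatment". Two limbs follow.

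- Early limb: "If 3 or more patients in the first 15 treated patients experience a grade 3 or higher adverse event, besides acute dermatitis".
- Later limb, once 15 patients have been treated: the same kind of event in 20% or more of all patients.

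Both limbs count an event "that is at least possibly related to treatment within 90 days post treatment", and "The following rule will be evaluated for each arm separately". Section 10.53 equates grade 5 with death, so a death falls inside the grade 3-or-worse count. Neither limb has a separate grade 5 threshold.

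The same section adds three qualifications. "The study team may choose to suspend accrual because of unexpected adverse event profiles that have not crossed the specified rule below". The rule itself may be changed during the trial in the light of new adverse event information. A closing note says that "we will review grade 4 and 5 adverse events deemed" unrelated or unlikely to be related, in order to check attribution and pick up unrecognised treatment effects.

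Elsewhere, section 10.1 makes any death a serious adverse event. Section 10.61 sends serious events to sentinel-event follow-up. Section 10.3 has the sponsor-investigator evaluate each event and gives 5 working days for telling the IRB of one judged a UPIRTSO. Sections 10.62 and 16.71 have the DSMB review safety a minimum of two times a year.

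**The concern.** A rule that pools grades 3, 4 and 5 is designed to detect an excess rate of serious toxicity. It is a poor detector of a few deaths, because each death moves the count no more than a grade 3 event does. The treatment here is adjuvant, and the two proton cohorts described in section 1.2 mention isolated grade 3 events and no grade 4 or 5 event. One related death would lie well outside what the plan describes.

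What is at stake is whether randomisation continues between a related death and the next independent look. Section 16.4 plans up to 96 patients over 3 years. With even accrual and two DSMB reviews a year, 96 / 3 / 2 = 16 more patients could be randomised between reviews. The decision to pause before then would lie with the study team of an open-label trial.

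**Working it through.** **Inputs.** From 16.72: 3 of the first 15; 20% thereafter; assessed at any time; each arm separately. From 16.4: 82 patients treated at 1:1, so about 82 / 2 = 41 per arm. The plan states no operating characteristics for this rule, so there is no probability of its own to reproduce.

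**Step 1: the thresholds agree.** 3 / 15 = 20.0%, so both limbs use the same rate. After patient 15 the smallest count that triggers is 0.20 × n, rounded up.

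**Step 2: counts that do not trigger.**
- First 15 in one arm: 2 / 15 = 13.3%, below 3.
- First 15 in each of two arms: 2 + 2 = 4 of 30, since the arms are judged separately.
- Late in an arm: 7 / 40 = 17.5%. The limit is 8 for n = 36 to 40 (8 / 40 = 20.0%). Because 7 / 35 = 20.0% would trigger, this example needs the seventh event to become known after patient 35, with every earlier limit also respected.

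**Step 3: how often the rule fires.** Let p be the per-patient risk of a related death within the window, and assume no other qualifying events. The documents give no value for p; the range is illustrative. Counts only rise, so crossing at any time up to patient 15 is the same as having 3 or more at patient 15:

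P(fires) = 1 − [(1−p)^15 + 15p(1−p)^14 + 105p²(1−p)^13]

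P(at least one related death) = 1 − (1−p)^15

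At p = 0.05: P(fires) = 1 − (0.4633 + 0.3658 + 0.1348) = 0.036; P(at least one) = 1 − 0.4633 = 0.537.

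| Assumed p | Rule fires by patient 15 | At least one related death by patient 15 |
|---|---|---|
| 1% | 0.04% | 14% |
| 2% | 0.3% | 26% |
| 5% | 3.6% | 54% |
| 10% | 18.4% | 79% |

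An exact recursion over the later limb, with no reporting lag, gives 0.3% at p = 2% and 4.1% at p = 5% by patient 41. The chance of at least one related death by then is 1 − 0.98^41 = 56% and 1 − 0.95^41 = 88%.

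**Step 4: sensitivity to other toxicity.** If the total rate of related grade 3-or-worse events (deaths included) were 10%, 15% or 20%, also assumed, the rule would fire by patient 15 with probability 18.4%, 39.6% or 60.2%, and by patient 41 with probability 23.4%, 52.5% or 77.7%. The figures in step 3 are therefore a lower bound for a given death risk.

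**Step 5: other provisions.** Sections 10.1, 10.3, 10.61, 10.62, 16.71 and the rest of 16.72 were read for any duty to pause accrual, or to convene the DSMB, after a related death. None contains one.

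**The case against.** The strongest reply is that pooling is a legitimate choice, no passage contradicts another, and the plan surrounds the rule with other safeguards. Much of this stands, and it rules out several stronger readings that a reader might infer.

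- That accrual stays open after two related deaths. The text supports only that suspension is not required. The study team may pause below the threshold, and the rule may be revised at any time.
- That a related death is merely tallied. It is a serious adverse event with sentinel-event follow-up and sponsor-investigator evaluation, and it goes to the IRB within 5 working days if judged a UPIRTSO.
- That the closing note of 16.72 reviews unrelated deaths more carefully than related ones. Its stated purpose is to verify attribution, which is not in doubt for events already called related.
- That 8 of 41 in an arm would pass. The snapshot is below the limit (8 / 41 = 19.5%), but 8 known at patient 40 already triggers, and 41 is about the whole planned arm. With no reporting lag, ending at 8 of 41 uncrossed has probability of at most about 0.7% for assumed event rates of 1% to 30%.
- That the rule conflicts with the figure of at most 1% in 16.4. That sentence, "The rate of grade 3 or greater late toxicity in this population is expected to be", concerns late events, which 16.2 places after the first 90 days. The rule covers the period up to 90 days, so the figure does not calibrate it.

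It is also fair to say that deaths with no accompanying grade 3 or 4 toxicity are an extreme scenario, and that a single death rated possibly related may be coincidental. The first point is why step 4 is shown. The second is a reason for independent review, not a reason to leave the pause optional.

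**Conclusion.** The point holds as a gap in a safety rule, not as an internal contradiction. The only mandatory accrual trigger weights a related grade 5 event and a related grade 3 event equally. Two related deaths in an arm's first 15, with no third qualifying patient, do not require suspension. Nothing else in the plan obliges an accrual hold or a DSMB review before the next routine one.

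Under an assumed related-death risk of 2% to 5% with no other qualifying events, the rule fires by patient 15 with probability 0.3% to 3.6%, against 26% to 54% for at least one related death. These figures rest on that assumption and on immediate reporting. The 2-of-15 result needs neither, since it follows from the wording alone. The matter merits a cheap improvement and does not affect the trial's efficacy or safety analyses.

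**What to change.** Add one bullet to 16.72: any grade 5 event within the rule's existing 90-day window that is at least possibly related to study treatment temporarily suspends accrual until the DSMB has reviewed it. Leave the 3-of-15 and 20% counts as they are. The closing note on unrelated grade 4 and 5 events need not change. The bullet concerns accrual and board review only, not any patient's treatment.

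The cost is a short protocol amendment, with no extra patients or data. The downside is a brief accrual pause whenever such a death occurs. Its probability in an arm's first 15 patients is the right-hand column of the table, for example 14% at an assumed risk of 1%, and lower if the true risk is smaller.
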